8 POINT OF ENROLLMENT AND EXIT

The study will be conducted in accordance with ISO 14155:2020 and in compliance with national and local laws in the geographies the study will be conducted.

8.1 Point of Enrolment

Subjects are considered enrolled in this study at the time the Informed Consent process has been completed. In the event of subject withdrawal or discontinuation prior to study completion, study subjects will not be replaced.

8.2 Point of Exit

Study subjects may exit the study for a variety of reasons. The Investigator shall record the reason for study exit in the applicable Study Completion CRF. These reasons include, but are not limited to:

- Study completion.
- Withdrawal by the Subject.
- Withdrawal by the Investigator.
- Lost to follow-up.
- Death.
- Study Termination.

Data collected until the last known contact of study subject may be used in the analysis of study data. For study subjects lost to follow-up, the Investigator shall make three (3) documented attempts before confirming the subject is lost to follow-up. If the study subject withdraws from the study for any reason and there is an ongoing safety event, additional safety event information may need to be collected by the Investigator and shared with the Sponsor.

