5 POPULATION AND DURATION OF THE STUDY

It is proposed that the study is conducted in Poland, Germany, and Colombia. Additional sites in additional countries may be recruited. The study sample will be recruited from the Investigators available clinical population.

Individual subject duration of participation in the study is up to 12 weeks. It is anticipated enrolment will take 12 months and the overall study duration is anticipated to be approximately 18 months.

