10.2 Visit 2: Day 14 (+/- 2 days)

The following procedures and data are collected at this visit. All information on this visit is required. Crossover to the non-randomized study dressing is not permitted.

- Review of concomitant medications, documenting any changes (medication used, route, dose, unit, frequency, indication, start date, stop date or ongoing)
- Wound assessment
 - Wound size (measured in cm at the longest point and across the widest point, as well as depth)
 - Wound bed appearance
 - Exudate level, colour and consistency
 - Condition of peri-wound skin
 - Maximum pain level on a scale of 0 to 10 within the last 24 hours

- Level of odour on a scale of 0 to 10 for the study participants and mild/medium/strong for the clinician.
- Therapeutic Index for Local Infections (TILI) score
- Number of days, since last visit, where compression was not applied (including documentation of reason for no compression)

A clinician decision is required at this visit regarding continuation of the randomised dressing (AQUACEL® AG+ Extra™ or Cutimed® Sorbact®) or transition to long-term management per standard of care. In subject with multiple study wounds the decision is made for each study wound separately. For example, one wound can be selected for Option 1 and another wound for option 3.

Option 1: An additional 14 days of treatment with randomised dressing (AQUACEL™ Ag+ Extra™ or Cutimed® Sorbact®) is required.

Option 2: Further treatment with randomised dressing is not indicated. The wound should be further managed per standard of care.

Option 3: Clinician determines that a non-standard of care treatment is needed. Treatment with the randomised dressing is discontinued.

Regardless of the option chosen, the subject remains in the study and is followed-up until the study exit (see section 8.2)

Once the decision has been made on the treatment option, the following information will be collected.

- Dressing application according to clinician decision (randomised dressing or other dressing) (name, size and lot number is recorded)
- Documentation of any additional products used
- Document any additional therapies
- Document and address any Adverse Events
- Document and address any Serious Adverse Events
- Number of intermediate visits where dressings were changed between scheduled visits (this is the number of times a subject received a new dressing since the last visit)
- Wound-QOL-14 (only if Option 2 or 3 has been selected).

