18.1 Alpha Value

Alpha value will be 0.05 for both one-way and two-way testing.

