18.2 Statistical Approach for the Primary Endpoint

The study hypothesis is that the Experimental Treatment with AQUACEL® Ag+ Extra™ will have similar effectiveness to the Control Treatment with Cutimed® Sorbact® in proportion of wounds that have completely healed by 84 days. The statistical hypothesis is that Experimental Treatment with AQUACEL® Ag+ Extra™ will be non-inferior to Control Treatment with Cutimed® Sorbact® in proportion of wounds that have completely healed by 84 days.

The statistical null and alternative hypotheses are as follows:

$$\begin{aligned} H_0: \pi_{Exp} - \pi_{Con} &\leq \delta \\ H_A: \pi_{Exp} - \pi_{Con} &> \delta \end{aligned}$$

where π_{Exp} and π_{con} represent the true proportion of target wounds that have healed by 84 days in patients treated with AQUACEL® Ag+ Extra™ and Cutimed® Sorbact®, respectively, and δ is the non-inferiority margin. The non-inferiority margin (δ) is set to -15%.

The statistical definition of success is the rejection of H_0 . The null hypothesis (H_0) will be tested by constructing a two-sided 90% confidence interval for the difference in the proportions of ulcers that have completely healed between the Experimental Arm and the Control Arm. If the lower boundary of the interval does not include δ , then the null hypothesis will be rejected. If non-inferiority of AQUACEL® Ag+ Extra™ to the Cutimed® Sorbact is demonstrated, its superiority will be tested.

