18.4 Sample Size Determination

Under the assumption that the proportion of completely healed ulcers by day 84 is 0.8 (80%), the sample size of 206 subjects and minimum of 206 wounds randomized 1:1 to Experimental and Control arms will have 85% power to reject the null hypothesis.

Sample size assumptions concerning the proportion variance and average number of wounds per subject will be verified during the study in a blinded fashion. Such verification does not inflate alpha-value.

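### Section 8.2 makes no provision to learn whether a wound still open at an early exit had closed by Day 84, so the primary outcome is unknown for those subjects

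*Combined protocol and SAP*

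**What the plan says.** The hypothesis in section 18.2 is that the experimental dressing "will be non-inferior to Control Treatment with Cutimed® Sorbact® in proportion of wounds that have completely healed by 84 days". Each wound's status at or before Day 84 is therefore the primary outcome.

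**Staying in the study.** Section 10.2 says of the Day 14 treatment decision: "Regardless of the option chosen, the subject remains in the study and is followed-up until the study exit (see section 8.2"). Section 10.3 says the same of whatever treatment follows Day 28. Both sentences defer to section 8.2 for when follow-up ends.

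**Leaving the study.** The list of exit reasons in section 8.2 is expressly not exhaustive. One entry is "Withdrawal by the Investigator", with no criteria; the reason for exit must be recorded. The section does not separate stopping the dressing from leaving the study. Data up to the last contact may be used, and three contact attempts come before a subject is declared lost. On later information its only sentence begins: "If the study subject withdraws from the study for any reason and there is an ongoing safety event, additional safety event information may need". It has no matching provision for wound closure.

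**What limits the gap.** Section 10.6 calls for a study exit visit whatever the reason for exit, and Table 9.3-1 marks a wound assessment there. Section 17.3 has the sponsor routinely review the number of withdrawn subjects.

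**Replacement.** Section 8.1 says subjects who leave are not replaced.

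**The concern.** A subject who exits at, say, week 5 with an open wound has a known status at week 5 but an unknown status for the primary outcome. The wound may or may not close in the remaining seven weeks, and the protocol asks nobody to find out. In some cases the answer may be within reach: section 5 says "The study sample will be recruited from the Investigators available clinical population", and section 2.6 describes follow-up as standard of care.

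The trial is open-label (section 3.1), so the decision to withdraw a subject could depend on the arm. The main test is for non-inferiority, where a bias that shrinks a real deficit favours success. Loss of outcome data also costs power in a design that has none to spare.

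**Working it through.** **1. The plan's sample size.** Inputs: margin 15 points and "constructing a two-sided 90% confidence interval for the difference in the proportions of ulcers that have completely healed" (section 18.2), which corresponds to one-sided 0.05; section 18.1 agrees ("Alpha value will be 0.05 for both one-way and two-way testing"). Section 18.4 gives 80% healed, read here as applying to both arms, 1:1 allocation and 85% power. One wound per subject is assumed.

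n per arm = (z₀.₉₅ + z₀.₈₅)² × [0.8×0.2 + 0.8×0.2] / 0.15² = (1.645 + 1.036)² × 0.32 / 0.0225 ≈ 102.3, rounded up to 103.

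The total is 206, the stated figure, and power at 103 per arm is 85.2%. So 206 contains no allowance for missing outcomes.

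**2. Cost in power.** The documents give no exit rates, so the rates here and below are assumptions. If leavers are dropped and leaving is unrelated to healing, the effective n per arm is 103 × (1 − d):

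| Loss d | n per arm | Power |
|---|---|---|
| 0% | 103 | 85.2% |
| 10% | 92.7 | 81.8% |
| 20% | 82.4 | 77.7% |

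**3. Bias in a complete-case difference.** Let 80% close among subjects with known status in both arms, so the apparent difference is 0. Let fractions a (experimental) and b (control) exit with an open wound, of whom a proportion q close by Day 84 (q_E and q_C where the arms differ). The true difference is [(1−a)×0.8 + a×q] − [(1−b)×0.8 + b×q].

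- a = 0.12, b = 0.04, q = 0: 0.704 − 0.768 = **−6.4 points**.
- a = 0.12, b = 0.04, q = 0.3: (0.704 + 0.036) − (0.768 + 0.012) = 0.740 − 0.780 = **−4.0 points**.
- a = b = 0.10: (0.72 + 0.10×q_E) − (0.72 + 0.10×q_C), which runs from −10 to +10 points. These are extreme bounds: all leavers close in one arm and none in the other.

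**4. The direction is not fixed.** At the null boundary (65% v 80% true closure) the nominal one-sided error is 5%. The chance of a false non-inferiority claim is Φ[(0.15 + D)/SE − 1.645], where D is the expected observed difference and SE its standard error.

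| Assumed loss and handling | D | Error |
|---|---|---|
| 10% in experimental arm only, leavers close at 20%, complete cases | −10.0 points | 20.2% |
| Same, leavers close at 40% | −12.2 points | 11.5% |
| 10% in both arms, leavers close at 20%, complete cases | −16.7 points | 2.7% |
| 10% in both arms at random, missing counted as not healed | −13.5 points | 7.8% |

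For example, row 1 has observed experimental closure (0.65 − 0.10×0.2)/0.90 = 0.70 against 0.80. Row 3 has 0.70 against (0.80 − 0.02)/0.90 = 0.867. Depending on who leaves and how missing values are handled, the same amount of missing data can make the test too lenient or too strict.

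**The case against.** The strongest reply is that the protocol already does most of what is needed. The exit visit records wound status whatever the reason for leaving. A subject whose wounds had all closed by then has a known outcome. Only closure after exit is lost. This is correct and limits the point.

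Four stronger readings are tempting, and the documents support none of them:

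- **That investigators may withdraw subjects without limit.** Section 8.2 states no criteria, but silence is not a grant of discretion. The reason must be recorded, and section 17.3 has the sponsor review withdrawals.
- **That a subject who stops the dressing before Day 14 drops out of follow-up.** Nothing makes that stop an exit. The subject is still due at Visit 2, where Options 2 and 3 cover ending the randomised dressing and the stay-in-study sentence applies. What remains is an early stop that a site processes as an exit because section 8.2 does not distinguish the two.
- **That no analysis can recover the loss.** If no leaver closes, counting leavers as not healed returns exactly the true −6.4 points in the 12% v 4% example. If 30% close, the same rule still returns −6.4 when the truth is −4.0, an error of 2.4 points against the experimental dressing. An imputation rule can therefore be right, but only when its assumption is.
- **That the loss favours non-inferiority.** That needs unequal exits and a complete-case analysis, or another unfavourable combination. Section 18.7 defines a Completed Cases population that keeps early leavers only if all their wounds healed, but the protocol does not name it as the primary analysis set. The separate SAP to which section 18 refers is not in the supplied text and may give a rule for missing status.

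Two practical objections also stand in part. Section 5 says where subjects are recruited, not where they are treated after leaving, so availability of a clinic record is an inference. Closure means full epithelialisation (section 4.2.1), and a telephone report in an open-label trial is weak evidence of that. The remedy should allow for both.

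**Conclusion.** The point holds in a limited form. For a subject who exits before Day 84 with an open study wound, the plan obtains status at exit but does not seek closure by Day 84. Following section 8.2 as written thus leaves the primary outcome unknown in some cases where it might be obtained. The sample size leaves no room for this: 206 reproduces exactly with no dropout allowance, and leavers are not replaced.

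How much this matters cannot be determined from the supplied text. With the assumed 12% v 4% exits, a complete-case difference of 0 conceals −4.0 to −6.4 points, roughly a quarter to two-fifths of the 15-point margin (4.0/15 = 27%; 6.4/15 = 43%). With equal loss of poor healers the complete-case test is conservative (about 2.7% error at 10% loss). These figures treat each subject as having one wound and rest on assumed exit and closure rates. A missing-data rule in the SAP could reduce the bias, but it would still substitute an assumption for an outcome that could sometimes be observed. This is an inexpensive improvement that should be made, not a flaw that invalidates the design.

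**What to change.** 1. **Retrieve the outcome.** In section 8.2, state that for each subject who exits before Day 84 with an open study wound and has not refused further data use, the site records closure status as of Day 84 (closed or open, with the date if closed). The source is the clinic record or an examined wound where available, and each entry is flagged by source. These data enter the primary analysis. Status known only by telephone is recorded and used in a sensitivity analysis.
2. **Align section 8.2 with sections 10.2 and 10.3.** State that stopping or switching the randomised dressing at any time, including before Visit 2, does not by itself end follow-up. This concerns data collection only and changes no treatment rule.

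**Cost.** Protocol wording, a CRF field, a line in the consent form, and one record check or call per early exit. Status will remain unobtainable for deaths, refusals and true loss of contact, so a missing-data rule is still needed. Closure established remotely is less certain than closure of an examined wound, hence the source flag.

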8.3 Completed Subject

Subject has completed the study if the subject has completed the final study visit (84 days follow-up visit) or earlier if all study wounds have healed prior to 84-day follow-up visit. If subject has multiple wounds, the subject exits the study when the last study wound heals or when subject attends the final study visit, whichever occurs first. Study completion can occur between the scheduled study visits.

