3 DESIGN OF CLINICAL INVESTIGATION

3.1 Study Design

The study is a post market, multi-centre, randomised, open label, global prospective study to compare the performance of AQUACEL® Ag+ Extra™ and Cutimed® Sorbact® dressing in the management of patients with venous leg ulcers (VLUs).

The VLUs will be treated with AQUACEL® Ag+ Extra™ (Experimental Arm) or Cutimed® Sorbact® (Control Arm) for up to 4 weeks. The WLUs will then be managed the with Standard of Care for up to 10 weeks, or until the wound has healed or the dressing is no longer clinically indicated. Crossover of dressings is not permitted.

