3.3 Minimisation of Bias

Bias in studies can impact results in any study. To minimise bias, the following steps, which include, but are not limited to, have been taken:

- Multiple sites and geographies have been selected, which reduces the instrumentation and performance biases.
- Randomization minimizes confounding bias.

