4.2 Endpoints

4.2.1 Primary Endpoint

- Complete wound closure as defined by 100% epithelialisation of the wound surface (Gould 2019).

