10.6 End of Study Visit (Study Exit)

The study exit visit will occur when:

- the subject exits the study for any reason, including that all study wounds have healed; or
- The subject attends Visit 7.

Completion of end of study or appropriate forms is required.

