18.7 Statistical Populations

All subjects that are randomized are considered participants.

Safety Population includes all subjects that are randomized to and receive one of the study treatments.

Full Analysis Data Set. This will be constructed following the Intent-to-Treat (ITT) principle and will include all subjects that are randomized, receive one of the study treatments, and have at least one follow-up visit after the baseline (Visit 1).

Per Protocol Population (PP) This will all subjects that are randomized, receive one of the study treatments, do not discontinue the trial prior to 4-week follow-up visit except for the reason that all study ulcers have closed and have no major protocol deviations that would impact integrity of the statistical analysis of primary endpoint.

Completed Cases (CC) Population is a subset of Full Analysis Data Set Population and includes all subjects who have the final study visit (Day 84) or have exited the study earlier due to all study wounds have healed.

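### Follow-up ends at an unconfirmed, open-label call that all study wounds have healed, so a false or short-lived final closure counts as healed and can bias the non-inferiority test in an unknown direction

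*Combined protocol and SAP*

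**What the plan says.** The primary endpoint in section 4.2.1 is "Complete wound closure as defined by 100% epithelialisation of the wound surface". It has no confirming visit and no minimum time closed. Section 18.2 analyses it as the proportion of wounds healed by 84 days.

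Section 8.3 sets the exit rule. Any subject is complete at the Day 84 visit, "or earlier if all study wounds have healed prior to 84-day follow-up visit". For subjects with several wounds, "the subject exits the study when the last study wound heals", or at the final visit if that comes first. It adds: "Study completion can occur between the scheduled study visits". Section 10.6 matches: the exit visit takes place when "the subject exits the study for any reason, including that all study wounds have healed". In section 18.7 the Completed Cases set includes subjects who "have exited the study earlier due to all study wounds have healed".

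Section 3.1 describes a "multi-centre, randomised, open label, global prospective study". Section 3.3 names two bias controls, multiple sites and randomisation ("Randomization minimizes confounding bias"), and says its list is not exhaustive. No blinded or independent assessment of closure is described. Section 11.2 records adverse events only up to the subject's final visit.

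**The concern.** One judgement, made by staff who know the dressing, does two things at once. It scores the primary outcome as a success, and it removes the subject from the only follow-up that could show the judgement was wrong. The End of Study column in Table 9.3-1 does include a wound assessment, but that is the exit visit itself and not a later check.

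Wounds are also not observed alike. A single wound, or the last wound to close in a subject with several, gets no later look. A wound that closes earlier in a subject with several stays under observation until the last one closes or Day 84.

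At stake is the non-inferiority conclusion. Misclassified closures can shrink or widen the difference between arms, and no analysis rule written later can recover assessments that were never made. The same exit rule makes adverse event follow-up shorter for subjects who heal sooner, so crude incidence is not counted over equal time if the arms heal at different speeds.

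**Working it through.** **Inputs from the protocol.** Healing rate 0.80, 206 subjects randomised 1:1 and 85% power (18.4); margin -15 points and two-sided 90% confidence interval (18.2).

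**Assumptions.** The documents give no rate of false or short-lived closure, so those below are ranges. One wound per subject, no clustering, no dropout.

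**1. The plan's own figure.** With the same rate p in both arms, n per arm = 2p(1-p)(z0.95 + z0.85)²/0.15² = 0.32 × (1.645 + 1.036)²/0.0225 = 102.2, so 103 per arm and 206 in total. Power at 103 per arm is 85.2%. The stated sample size reproduces.

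**2. Baseline error rate.** Put the true difference at the margin, 65% experimental v 80% control. Summing the binomial probabilities of all outcome pairs in which the lower limit of a Wald 90% interval exceeds -15 points gives 5.1%.

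**3. Patterns of error.** Observed rates, with the chance of falsely declaring non-inferiority:

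- A. A share f of truly unhealed wounds is called closed in both arms. Observed rate = p + f(1-p).
- B. The same, in the experimental arm only: 0.65 + 0.35f v 0.80.
- C. The same, in the control arm only: 0.65 v 0.80 + 0.20f.
- D. A share r of called closures is short-lived, equal in both arms. Lasting closure is 55% v 70% (also -15 points, 5.1% baseline). Called rate = lasting rate/(1-r).

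| Pattern | 5% | 10% | 20% |
|---|---|---|---|
| A: observed difference, points | -14.25 | -13.5 | -12.0 |
| A: false non-inferiority | 6.6% | 8.4% | 13.3% |
| B: false non-inferiority | 8.9% | 14.6% | 32.5% |
| C: false non-inferiority | 3.6% | 2.5% | 1.0% |
| D: called difference, points | -15.8 | -16.7 | -18.75 |
| D: false non-inferiority | 4.0% | 2.8% | 1.1% |

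Example for A at f = 10%: 0.65 + 0.10 × 0.35 = 0.685 and 0.80 + 0.10 × 0.20 = 0.820, a difference of -0.135. If each arm gains the same absolute number of false closures, the difference is unchanged and the error rate stays at about 5%.

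**4. Unequal re-opening.** Let 80% be called closed in each arm, with re-opening of 10% of closures in the experimental arm and 5% in control. Lasting closure is 0.80 × 0.90 = 72% v 0.80 × 0.95 = 76%, a 4-point deficit the design cannot see. The chance of declaring non-inferiority is 85% on called closure and 57% on lasting closure. Swapping the arms reverses the sign.

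**5. Price of a confirmed endpoint.** If confirmation lowers the common rate, power at 206 and the total needed for 85% are: 0.80, 85.2% and 206; 0.75, 80.0% and 240; 0.70, 75.9% and 270.

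**The case against.** The strongest reply is that the direction is not known. A reader might infer that the exit rule biases the test towards non-inferiority. The documents do not support that: it holds for patterns A and B, fails for C and D, and is neutral for equal absolute numbers. Nothing in the protocol says which applies. This part of the objection stands in full. It does not remove the problem, because the design also gives no means of finding out.

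A reader might also confine the problem to subjects with one wound. The text does not support that either. The sentence on the last study wound concerns subjects with several wounds, the general rule is the sentence before it, and the last wound to close has the same gap.

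It can further be said that healed by 84 days may mean first closure, so that a re-opening seen in a subject with several wounds changes nothing. The supplied text does not say how such a wound is classified, and section 18 defers detail to an SAP that is not in that text. So unequal observation is established, but unequal scoring is not. This reply does not cover false calls: a wound that was never closed is an error under any definition.

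Lastly, a confirming visit is made by the same unblinded staff and shows nothing after it. That is correct and limits what the fix can claim. It is also why confirmed closure is better placed first as a sensitivity analysis than as a replacement endpoint.

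**Conclusion.** The point holds as a gap in verification. Sections 8.3 and 10.6 end follow-up at an open-label closure call that is never checked, for every single wound and for the last wound to close in subjects with several. The non-inferiority test can be biased, in an unknown direction. Across the assumed patterns and error rates of 5% to 20%, false non-inferiority ranges from about 1% to 32.5% against a baseline of 5.1%. The largest values need over-calling in the experimental arm alone, which the documents neither show nor guard against.

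The sample size is not in error: 206 follows from the stated inputs. The figures rest on assumed error rates and one wound per subject. A confirmation rule in material not supplied cannot be excluded, but exit at healing would leave it no later data to use.

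**What to change.** 1. Amend 8.3, 10.6 and the matching Completed Cases wording in 18.7. A subject whose wounds have all closed stays in follow-up until a scheduled visit about 14 days after the closure call, or Day 84 if sooner. State a minimum gap, so that a visit a day or two after an between-visit closure does not count as confirmation. Assess every study wound by the same rule, and state how a wound that closes and re-opens is scored.
2. Pre-specify closure confirmed at that visit as a key sensitivity analysis of the primary endpoint. Count closures first seen too late to confirm as observed, then leave them out in a second run. State the rule for a missed confirming visit.
3. If confirmed closure is made the primary endpoint instead, restate the power in 18.4 for the expected confirmed rate: with 206 subjects, about 85% at 0.80, 80% at 0.75 and 76% at 0.70.
4. Summarise adverse events per subject-week as well, because follow-up length depends on healing.

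The cost is a protocol amendment and, for early closers, usually one extra visit that is already in the schedule. The confirmed closure rate will be somewhat lower than the called rate. The confirming assessment remains unblinded, and re-opening after it is still not seen.
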